### 8.6.3. Treatment Patterns

- **Non-persistence.** A 0/1 flag will be created to identify if the patient is not persistent with tofacitinib before the end of the 12 month follow-up period.

Non-persistence will be identified based on a gap in treatment with the index medication or switching to another biologic.

Among patients with 1 year of follow-up, persistence through the end of the 1 year follow-up will be identified. Persistence will be identified based on the day supply (or presumed day supply) and fill dates of claims for the index medication (see [Table 2](#) for a listing of presumed day supplies). Persistence with the index medication will be defined as not having a gap in therapy of at least 60 days between fills/infusions. For retail pharmacy (RX) claims the day supply will be utilized. For Healthcare Common Procedure Coding System (HCPCS) claims a presumed day supply derived from the product label will be utilized. A gap of at least 60 days between the run-out date (service date + day supply-1) and the next service date will be considered non-persistence. Patients with early refills will be allowed to accumulate a stockpile of the index medication of up to 14 days for later use.

- **Post persistence treatment patterns.** Patients who are not persistent for the entire follow-up period will be classified into the following mutually exclusive categories based on the first occurrence of non-persistence: switch immediately, discontinue then restart, discontinue then switch, discontinue and never switch or restart.
  - **Switch immediately.** Patients will be classified as switching immediately if they initiate a non-index biologic before a 60-day gap in treatment is observed for the index medication.
  - **Discontinue then restart.** Patients will be classified as discontinuing and then restarting if there is a gap in the index therapy of at least 60 days and the first medication observed after the gap is the index medication.
  - **Discontinue then switch.** Patients will be classified as discontinuing and then switching if there is a gap in the index therapy of at least 60 days and the first medication observed after the gap is a biologic (including Tofacitinib) different from index medication.
  - **Discontinue without switch or restart.** Patients will be classified as discontinuing without switch or restart if they have a gap in therapy of at least 60 days and there are no claims for either the index med or a different biologic for the remainder of the follow-up period.
- **Switch any time.** In addition to the 4 mutually exclusive treatment patterns, patients with a switch medication any time during the 12-month follow-up period will be identified.

- **Restart any time.** In addition to the 4 mutually exclusive treatment patterns, patients who have a claim for the index medication any time after they are considered non-persistent with the index treatment (ie, including after switching) during the 12-month follow-up, will be identified.
- **Medication Possession Ratio (MPR):** In addition to the adherence measure in the medication effectiveness assessment (see [Section 8.6.4](#)), the MPR will be evaluated for persistent patients as the total days supply between the first and including the last prescription/administration divided by the time between the first through and including last biologic prescription/administration days supply. Adherent patients will be considered those with  $MPR \geq 0.8$ . For MPR calculations, multiple prescriptions having same fill date will be treated as one prescription with longest days supply; and for all prescriptions days supply will be capped at end of follow-up. Also, the MPR will be capped at 1.0.
- **NB-DMARD adherence/addition.** Adherence with MTX and addition of a non-biologic DMARD other than MTX (sulfasalazine, hydroxychloroquine, leflunomide) during the 12 month follow-up will be identified.
  - **MTX adherence.** A single measure of adherence (PDC) will be created using all claims for MTX during the 12-month follow-up period. Adherence will be calculated as the total day supply divided by the number of days from the first claim during the follow-up until the end of the follow-up.
  - **NB-DMARD addition.** Addition of a NB-DMARD will be evaluated.

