### 8.5. Period of Observation

All patients will be required to be continuously enrolled in the health plan for at least 24 months. Patients will have a variable length baseline period of at least 12 months. The 12 months prior to the index date will be used to assess the majority of pre-index characteristics. However, for select measures, eg, number of prior biologic therapies, and years since first RA diagnosis, the entire variable length baseline period will be utilized.

Measures utilizing the variable length baseline are noted. All baseline periods will be censored at January 1, 2012. The twelve months following the index date will be used to assess outcomes including treatment patterns, and health care costs, utilization and medication effectiveness.

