#### **8.10.1. Descriptive Analysis**

All study variables, including pre- and post-index measures, will initially be analyzed descriptively. In general, numbers and percents will be provided for dichotomous and polytomous variables, while means, medians, and standard deviations will be provided for continuous variables. Missing or unavailable data will not be imputed.

Results will be stratified by treatment cohort, bivariate comparisons of pre- and post-index measures will be provided, and appropriate tests (eg, t-test, Mann Whitney-U test, chi-square test) will be used based on the distribution of the measure. The analysis that is performed (ie, the methods that are used and the patients who are included) will be specific the objective being examined. Descriptive techniques will be implemented for each objective.

Multivariable techniques (including effect decomposition) will be used when comparing outcomes and controlling for differences in patient characteristics between study cohorts.

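### Among tofacitinib discontinuers, the split into restart, switch or neither, and the Restart any time flag, depend on how much of the 12 months is left when the patient stops

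*Combined protocol and SAP*

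**What the plan says.** Section 8.5 fixes the outcome period from index: "The twelve months following the index date will be used to assess outcomes including treatment patterns". It also sets the enrolment rule: "All patients will be required to be continuously enrolled in the health plan for at least 24 months". With at least 12 months of baseline, this secures 12 months after index and no more.

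Section 8.6.3 defines tofacitinib non-persistence by a gap: "A gap of at least 60 days between the run-out date (service date + day supply-1) and the next service date will be considered non-persistence". Non-persistent patients are then placed in "mutually exclusive categories based on the first occurrence of non-persistence: switch immediately, discontinue then restart, discontinue then switch, discontinue and never switch or restart". Restart applies when "there is a gap in the index therapy of at least 60 days and the first medication observed after the gap is the index medication". The category for a switch after the gap has the same form, with a different biologic as the first drug seen. The last category applies when "there are no claims for either the index med or a different biologic for the remainder of the follow-up period". No minimum or common length of observation after the gap is set.

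Two supplementary flags follow. Switch any time covers the whole 12 months. Restart any time counts a tofacitinib claim at any point after non-persistence, up to month 12.

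Section 8.10 says that treatment patterns will be summarised across the cohorts. Section 8.10.1 adds that "numbers and percents will be provided for dichotomous and polytomous variables", with chi-square or similar tests. It does not say whether the percentages for these categories are taken among discontinuers or over the whole cohort. The possible multivariable outcomes in 8.10.2 are costs and medication effectiveness. The limitations in 8.12 do not mention the point.

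**The concern.** The restart rule has no time limit of its own: it asks only whether "the first medication observed after the gap is the index medication". The effective limit is the end of month 12, and the distance to that date depends on when tofacitinib ran out. An early stopper has most of the year in which to be seen restarting or switching. A late stopper has days, and is scored as neither almost regardless of what happens next.

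If percentages among discontinuers are read as behaviour after stopping, two things follow. Restart and switch are understated in every cohort. And if tofacitinib stops come later in one MTX cohort than in another, that cohort will show more apparent discontinuation without restart or switch even when patients behave identically after stopping. No time-to-event method, censoring or stratification by stop day is planned that would separate the two.

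**Working it through.** The plan gives no rate, sample size or stop-time distribution for this outcome, so there is no stated figure to reproduce.

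**Inputs from the plan**
- Outcome window: 12 months from index, taken as 365 days (8.5).
- Gap: at least 60 days after run-out (8.6.3).
- Earliest plausible run-out: about day 60. Two tofacitinib fills are required (8.2.1), and Table 2 rounds each supply to a multiple of 30 days with a minimum of 30.
- Latest run-out at which a 60-day gap is complete by day 365: 365 - 60 = day 305.

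**Assumptions, not in the plan**
- The same constant hazard of restart or switch after gap completion in every patient, with probability h = 5%, 10% or 20% per 30 days.
- Run-out days spread evenly within each band.

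**Step 1. Time left to see a restart or switch**, 365 - t - 60 = 305 - t for run-out day t:

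| Run-out day | 60 | 120 | 180 | 240 | 300 |
|---|---|---|---|---|---|
| Days left | 245 | 185 | 125 | 65 | 5 |

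This step needs no assumption about behaviour.

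**Step 2. Share of discontinuers scored restart or switch.** With λ = -ln(1 - h)/30, the share at run-out day t is 1 - exp(-λ(305 - t)). Averaged over a band from a to b it is

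1 - [exp(-λ(305 - b)) - exp(-λ(305 - a))] / [λ(b - a)].

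Example: h = 10% gives λ = 0.003512. For days 60-120 the share is 1 - (0.522 - 0.423)/(0.003512 × 60) = 0.53. For days 210-305 it is 1 - (1 - 0.716)/(0.003512 × 95) = 0.15.

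| h per 30 days | Days 60-120 | Days 120-210 | Days 210-305 |
|---|---|---|---|
| 5% | 31% | 21% | 8% |
| 10% | 53% | 39% | 15% |
| 20% | 80% | 64% | 28% |

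Within a row, behaviour after the gap is the same; only the stop day differs.

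**Step 3. Effect on a cohort contrast.** Take two cohorts with identical behaviour after stopping but different mixes of early (days 60-180) and late (days 180-305) run-out. A 60/40 versus 40/60 mix gives a spurious difference of 0.2 × (early - late). A 70/30 versus 30/70 mix gives 0.4 × (early - late).

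| h | Early | Late | 60/40 v 40/60 | 70/30 v 30/70 |
|---|---|---|---|---|
| 5% | 27.0% | 10.0% | 3.4 points | 6.8 points |
| 10% | 47.4% | 19.1% | 5.7 points | 11.3 points |
| 20% | 73.9% | 34.9% | 7.8 points | 15.6 points |

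With equal mixes the difference is zero at every h.

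**Step 4. Which measures are affected.**
- Non-persistence and Switch any time are counted over the same 12 months from index for everyone, so neither has the variable window.
- Switch immediately does not need a completed gap, so it has no post-gap window.
- Discontinue then restart, discontinue then switch, and neither have the variable window when expressed among discontinuers.
- Restart any time starts its window at non-persistence, so it has the variable window too.

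**The case against.** The strongest reply has four parts.

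- **Reach.** A reader might infer that the primary outcome itself is compromised. The documents do not support that. Persistence and switching are in the primary objective, but the specific patterns that 8.10 lists for it are non-persistence, opioid and NSAID receipt, and adherence to tofacitinib and to MTX. The four-way split is not on the list. Non-persistence has an equal 12-month window, and switching has an equal-window measure in Switch any time. If a cohort stays on tofacitinib longer and so switches less by month 12, that is a real 12-month difference. This stands.
- **Denominator.** Over the whole cohort, the four categories describe status at month 12 after equal follow-up and can be read as such. The short label says never, but the full definition limits the category to the rest of follow-up. This stands. The difficulty is confined to percentages among discontinuers and to Restart any time, and the plan leaves the denominator open.
- **Bias between cohorts.** A reader might also infer that the MTX cohort comparison is biased. The plan reports no tofacitinib stop times by cohort, so this is not shown. Equal stop times cannot be presumed either, since the cohorts are formed from MTX refill gaps in the same 12 months.
- **Remedy.** Comparing behaviour after stopping conditions on having stopped, which happens after index and may itself differ by MTX cohort. This stands and must be stated with the result. It applies equally to the planned percentages if they are taken among discontinuers.

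**Conclusion.** The point holds in a limited form. The dependence on stop day follows from the definitions in 8.5 and 8.6.3 alone: the post-gap window runs from about 245 days down to 5 and then to none. Its size rests on an assumed constant hazard. Across 5% to 20% per 30 days, the share scored as restart or switch is 31% to 80% for run-out on days 60-120, against 8% to 28% for days 210-305.

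The effect on a comparison of MTX cohorts is conditional. It is about 3 to 8 points with a 60/40 versus 40/60 mix of early and late stops, about 7 to 16 points with 70/30 versus 30/70, and nil if stop times are alike. Even then, percentages among discontinuers understate restart and switch. The mixes, like the hazards, are assumptions.

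Non-persistence, Switch immediately, Switch any time and whole-cohort 12-month status are not called into question. The change is worth making because it is cheap and the plan makes no allowance for the problem.

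**What to change.** In 8.6.3 and 8.10:

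1. State that the four categories are reported with the whole cohort as denominator, as status at 12 months.
2. For behaviour after stopping, compare cohorts on the cumulative incidence of restart and of switch from completion of the 60-day gap, treating the two as competing events and censoring at the end of month 12. Treat Restart any time in the same light, or label it as dependent on remaining follow-up.
3. Report the distribution of tofacitinib stop day by MTX cohort, so that the reader can see whether the condition for bias is present.
4. State that item 2 is a comparison among discontinuers, a subset formed after index, and is therefore descriptive.

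A fixed window is an optional alternative: for example, 90 days after gap completion among patients with run-out by day 215 (215 + 60 + 90 = 365). It is simpler, but it discards later stoppers, whereas the cumulative incidence keeps every discontinuer.

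The cost is SAP wording and one extra table or curve from claims already held. The remaining downside is that the new comparison is conditional on stopping and cannot be read as a causal contrast.

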## 1. LIST OF ABBREVIATIONS

Abbreviation	Definition
AE	Adverse Event
AHRQ	Agency for Healthcare Research and Quality
ARRA	American Recovery and Reinvestment Act
CIRAS	Claims-based index for RA severity
CMS	Centers for Medicare & Medicaid Services
COB	Coordination of benefits
COPD	Chronic obstructive pulmonary disease
CPI	Consumer price index
CPT	Current Procedural Terminology
ED	Emergency department
ER	Emergency room
FDA	Food and Drug Administration
GLM	Generalized linear model
HCFA	Care Financing Administration
HCPCS	Healthcare Common Procedure Coding System
HIPAA	Health Insurance Portability and Accountability Act
ICD-9 CM	The International Classification of Diseases, 9th Revision, Clinical Modification
IEC	Independent Ethics Committee
IRB	Institutional review board
ISPOR	International society for pharmacoeconomics and outcomes research
IV	Intravenous
MTX	Methotrexate
NB-DMARD	Non-biologic disease modifying antirheumatic drug
NDC	National Drug Code
NIS	Non-interventional study
NSAID	Non steroidal anti-inflammatory drug
PDC	Proportion of Days Covered
RA	Rheumatoid Arthritis
RAPID3	Routine assessment of patient index data
RX	Outpatient pharmacy
TNFi	Tumor-Necrosis Factor-alpha inhibitor
UB	Uniform Bill
US	United States

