### 8.3. Cohort Assignment

Patients will be assigned to a study cohort based on MTX status following initiation of combination therapy with tofacitinib and MTX. The “MTX discontinued” cohort will contain patients who experience a gap in MTX therapy of >60 days within 12 months post-index. The “MTX interrupted” cohort will contain patients who experience a gap in MTX therapy of >60 days with 1 or more subsequent fills within 12 months post-index. The “MTX persistent” cohort will contain patients with no gap >60 days within 12 months post-index. If sample size is insufficient, the MTX “discontinued” and “MTX interrupted” cohorts may be combined.

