#### 8.6.4. Medication Effectiveness

Among patients with at least one year of follow up, medication effectiveness at one year after the index date will be determined using the following six criteria. For each of the 6 criteria, a 0/1 flag will be created. Patients who are effectively treated for each of the 6 criteria will be considered effectively treated. Patients who fail any of the 6 criteria are therefore not effectively treated.

1. High adherence to index agent: a proportion of days covered (PDC) will be calculated based on total days supply over the 1 year follow-up. The PDC will be calculated by using the date of service and the day supply for each fill of the index medication. For patients that receive both 5mg and 11mg tofacitinb, both configurations will be treated interchangeably. Patients with early refills will be allowed to stockpile medications up to a maximum of 14 days total for later use.

---

 Curtis, J.R., et al., *Derivation and preliminary validation of an administrative claims-based algorithm for the effectiveness of medications for rheumatoid arthritis*. *Arthritis Res Ther*, 2011. **13**(5): p. R155.

 Oladapo, et. al. *Medication Effectiveness with the Use of Tumor Necrosis Factor Inhibitors Among Texas Medicaid Patients Diagnosed with Rheumatoid Arthritis*. *Journal of Managed Care Pharmacy*. 657 – 67. Vol. 20, No. 7. July 2014

2. No increase in dose for index medication compared to the starting dose. Dose escalation will be identified per the criteria listed in [Table 2](#).
3. No switching from the index medication to a (different) biologic agent or tofacitinib. A switch will be defined as use of a different biologic or tofacitinib any time during the follow-up period.
4. No adding of a new non-biologic DMARD to the index therapy. Adding a new non-biologic will be considered as having at least 1 claim for one of the 3 main:
  1. NB-DMARDs during follow-up and not having a claim for the same NB-DMARD during the baseline. Changing from 1 NB-DMARD at baseline to a different.
  2. NB-DMARD at follow-up will be considered as adding a new NB-DMARD, ie, failing the algorithm.
5. Oral glucocorticoids. Only National Drug Code (NDC) codes for oral glucocorticoids will be included:

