### **8.10. Data Analysis**

#### **Primary Objective**

- **To compare treatment patterns including dosing, concomitant medication use, adherence, persistence and switching** among tofacitinib+MTX patients who discontinue MTX vs. persist with MTX or experience interrupted MTX.

For this objective, treatment patterns will be summarized across the cohorts of interest. Specific treatment patterns include non-persistence with the index medication, receipt of an opioid, receipt of an NSAID, adherence with the index medication, adherence with MTX.

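### MTX adherence is called a PDC but defined as summed day supply over elapsed days, so it can exceed 1.0 and overstate adherence

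*Combined protocol and SAP*

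**What the plan says.** The MTX adherence bullet in Section 8.6.3 opens: "A single measure of adherence (PDC) will be created using all claims for MTX during the 12-month follow-up period". Section 1 expands PDC as "Proportion of Days Covered". The next sentence gives the formula: "Adherence will be calculated as the total day supply divided by the number of days from the first claim during the follow-up", with the interval ending at the end of follow-up. The bullet says nothing more about the calculation.

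Three other places matter for comparison.

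- **MPR, the bullet before the NB-DMARD item in Section 8.6.3.** Same-date fills are collapsed: "multiple prescriptions having same fill date will be treated as one prescription with longest days supply". Supply is truncated and the ratio bounded: "for all prescriptions days supply will be capped at end of follow-up. Also, the MPR will be capped at 1.0". The sentence holding the first two rules opens by limiting itself to MPR calculations, and the cap names the MPR.
- **Tofacitinib PDC, Section 8.6.4, criterion 1.** "The PDC will be calculated by using the date of service and the day supply for each fill of the index medication". Early refills may be stockpiled up to 14 days. Section 8.6.3 has a similar 14-day allowance for persistence, again for the index medication.
- **Use of the measure, Section 8.10, Primary Objective.** The listed treatment patterns include "adherence with the index medication, adherence with MTX".

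**The concern.** A proportion of days covered counts each calendar day once and cannot exceed 1.0. The MTX formula adds up everything dispensed and divides by elapsed time, so label and formula describe different quantities. A programmer following the formula and one following the label would report different results, and both could point to the protocol.

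Two kinds of excess supply enter the numerator, and they act differently across the cohorts of Section 8.3.

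1. **Supply running past month 12.** This arises only in patients with a fill late in follow-up: typically persistent patients, or interrupted patients, whose definition is "a gap in MTX therapy of >60 days with 1 or more subsequent fills within 12 months post-index". A patient who stopped, completed a gap of more than 60 days and never refilled cannot be affected. This part can therefore widen the cohort contrast.
2. **Same-day or overlapping fills.** These can inflate the value in any cohort, including patients who discontinued.

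**Working it through.** **Inputs.** The plan states no MTX adherence figure, so there is nothing to reproduce. From the documents: the MTX formula and the MPR rules (Section 8.6.3), the 14-day stockpile (Sections 8.6.3 and 8.6.4, index medication only) and the 12-month follow-up (Section 8.5). Assumed: a 365-day window, the fill patterns shown, and a first fill on day 0 unless stated.

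**Formulas.** Let d be the day of the first MTX claim in follow-up.

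- As written: W = (sum of day supply) / (365 − d).
- Days covered: C = (distinct days with supply from day d up to day 365) / (365 − d), with same-day fills collapsed to the longest.

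**Results on fixed patterns.**

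| Assumed fills | W, as written | C, days covered |
|---|---|---|
| 30-day fills on time, days 0 to 360 (13 fills) | 390/365 = 1.07 | 365/365 = 1.00 |
| 90-day fills on days 0, 90, 180, 270, 360 | 450/365 = 1.23 | 365/365 = 1.00 |
| Interrupted (75-day gap): 90-day fills on days 0, 90, 255, 345 | 360/365 = 0.99 | (90+90+90+20)/365 = 290/365 = 0.79 |
| No gap over 60 days: 90-day fills on days 0, 120, 240, 350 | 360/365 = 0.99 | (90+90+90+15)/365 = 285/365 = 0.78 |
| Stops after six 30-day fills, one same-day duplicate | 210/365 = 0.58 | 180/365 = 0.49 |
| Same, every fill duplicated (extreme) | 360/365 = 0.99 | 180/365 = 0.49 |
| Two consecutive 90-day fills, then stops | 180/365 = 0.49 | 0.49 |
| Interrupted (65-day gap): 30-day fills on days 0, 30, 60, 155, 185 | 150/365 = 0.41 | 0.41 |
| Persistent: 30-day fills on time through day 300 (11 fills) | 330/365 = 0.90 | 0.90 |

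The last three rows show that the two measures agree when fills neither overlap nor run past day 365.

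**Late fills alone.** With the first fill on day 0, one 90-day fill made with r days left adds (90 − r)/365:

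- r = 60: 30/365 = 0.08
- r = 30: 60/365 = 0.16
- r = 20: 70/365 = 0.19

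**Start day.** For a continuous filler with supply s per fill, W = s × ceil((365 − d)/s) / (365 − d). Over d = 0 to 30 this gives 1.00 to 1.08 (mean 1.04) for 30-day fills and 1.00 to 1.25 (mean 1.07) for 90-day fills. The correct value is 1.00 throughout.

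**Early refills.** Take seven 30-day fills made every 25 days, then a stop. W = 210/365 = 0.58. Distinct days depend on carry-forward:

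- none: 180/365 = 0.49
- limited to 14 days: 194/365 = 0.53
- unlimited: 210/365 = 0.58

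The carry-forward rule changes the answer, and the plan states none for MTX.

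**The case against.** The strongest counter-argument is that this is a terse definition, not an error. The tofacitinib criterion in Section 8.6.4 also describes its PDC in terms of total supply, and it too lacks a same-day, truncation or cap rule. The MTX sentence could be shorthand for the same calculation. The MPR truncation clause speaks of all prescriptions and might be meant to reach MTX. Section 8.11 provides for a programming plan and independent verification, where such details could be settled and values above 1.0 would be noticed.

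Part of this stands. The shorthand reading is possible, but the tofacitinib text goes on to specify fill dates and a stockpile limit, and the MTX text does neither. The truncation clause belongs to a sentence confined to the MPR. Even if it applied, overlap, same-day fills and the maximum would remain open. Verification against the protocol would confirm the formula as written, and overstatement below 1.0 would not stand out.

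The objections about size are fair. All fill patterns are assumed. The 90-day values of 1.23 and above need a fifth fill just before day 365, which happens for only 5 of the 31 start days (days 0 to 4). Duplication of every fill is extreme. For the early refiller, the written formula equals full carry-forward, so that case shows an unstated convention rather than a definite overstatement. Nor do start days 0 to 30 cover every eligible patient. Section 8.2.1 lets the initial MTX claim precede index by up to 30 days, so the first follow-up claim can come later. A day-90 start with 90-day fills gives 360/275 = 1.31.

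It is also true that little else depends on the measure, and that cohorts defined by MTX gaps will differ in MTX adherence under any definition.

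**Conclusion.** The concern holds. The stated formula is not a proportion of days covered. It exceeds 1.0 for patients who simply refill on time to the end of follow-up, and it overstates adherence below 1.0 in patterns that a cap alone would not correct. In the assumed examples the overstatement runs from nil to about 0.2 without duplicate claims (0.23 at most in the table). It is larger with many duplicates or with some later first claims. The true average is unknown because the documents contain no MTX fill data. The late-fill part can bias the cohort comparison; the direction and size of the duplicate-fill part across cohorts cannot be judged from the documents.

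The consequence is confined to one summarized outcome under the primary objective. Cohort assignment, the effectiveness algorithm and costs do not use it, and the plan sets no 0.8 threshold for MTX. The definition should be corrected before programming, but it does not threaten the study as a whole.

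**What to change.** In Section 8.6.3, define MTX PDC as the number of distinct days covered by MTX supply, built from the service date and day supply of each fill, from the first follow-up claim to the end of follow-up, divided by the days in that interval. Collapse same-day fills to the longest supply, as the MPR rule does. State how early-refill supply is carried forward, for example with the 14-day limit used for tofacitinib. Truncate supply at the end of follow-up. The measure is then at most 1.0 by construction.

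Optionally, note in the report that the cohorts are defined by MTX gaps, so differences in MTX PDC between them are partly built in.

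The cost is about two sentences and minor programming on data already held. Reported MTX adherence will be somewhat lower, and the carry-forward choice has to be fixed before the data are analysed.

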### 8.2.1. Inclusion Criteria

This study will include individuals who are privately insured and with Medicare Supplemental insurance paid for by their employers and initiating tofacitinib in combination with MTX for RA between 01 January 2014 and 31 January 2017. To be included in the final study sample, patients must meet the following inclusion criteria:

1. At least one claim for tofacitinib between 01 January 2014 and 31 January 2017 (the identification period).

- a. **Medication index date.** The index date will be the date of the first claim for tofacitinib during the identification period.

*Note: Patients will have a variable length baseline of at least a year long. The baseline period will be censored at January 1, 2012 based on licensed data availability. The majority of baseline measures will use data from the 12 months immediately prior to the index date. Select measures will use data during the entire variable length baseline.*

- b. Tofacitinib initiation. Patients must have a 2nd claim for tofacitinib within 60 days of the end of the days supplied from their index claim (at least two claims with no 60 day gap).
- c. Oral MTX initiation. Patients must have an initial prescription for oral MTX in the period between 30 days prior to index date and 30 days following index date followed by a 2nd prescription for oral MTX within 60 days of the end of the days supplied from their initial MTX claim (at least two claims/administrations with no 60 day gap).

2. Presence of The International Classification of Diseases, 9th Revision, Clinical Modification (ICD-9 CM) code for RA (in any position) during the one-year pre-index period or on the index date. ICD-9 = 714.0x-714.4x & 714.81 or ICD10 = M05.\* & M06.0\*-M06.3\* or M06.8\*-M06.9\*.

3. At least 18 years old as of the index date.

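### The MTX PDC counts only follow-up fills and starts at the first of them, so carried-in supply and early gaps are ignored, with a bias that depends on refill timing

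*Combined protocol and SAP*

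**What the plan says.** Section 8.6.3 (MTX adherence): "A single measure of adherence (PDC) will be created using all claims for MTX during the 12-month follow-up period". Total day supply is then "divided by the number of days from the first claim during the follow-up until the end of the follow-up".

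Section 8.2.1, criterion 1c, places the first oral MTX fill "in the period between 30 days prior to index date and 30 days following index date" and limits the delay before the next one. The fill that qualifies a patient for the combination may therefore precede index, and the next may come up to 60 days after run-out.

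Section 8.5: "The twelve months following the index date will be used to assess outcomes including treatment patterns". Section 8.3 defines the MTX cohorts by gaps; the discontinued "cohort will contain patients who experience a gap in MTX therapy of >60 days within 12 months post-index". Section 8.10 lists adherence with MTX among the treatment patterns for the primary objective.

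No rule carries pre-index MTX supply into follow-up. By contrast, the tofacitinib PDC in 8.6.4 is taken over the whole one-year follow-up, with a 14-day stockpile limit.

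**The concern.** When the initial MTX fill falls on days -30 to -1, three things happen at the start of follow-up.

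- Days after index covered by that fill leave both numerator and denominator. For a patient who later stops, covered days are removed and the uncovered days at the end are kept, so the value falls.
- Uncovered days between run-out of that fill and the first follow-up fill are also dropped, so the value rises.
- A patient with no MTX claim in follow-up has no value, and 8.10.1 says missing data are not imputed.

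The measure is compared across cohorts that are themselves defined by MTX gaps. A distortion that differs between stoppers and persisters changes that comparison. It also makes a patient's value depend on whether the first fill fell just before or just after index. This remains after overlapping fills, truncation at day 365 and a cap at 1.0 have been dealt with.

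**Working it through.** The plan gives no adherence figure to reproduce, so the check compares two formulas on the same records.

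**Inputs.** From the documents: initial fill on day -30 to +30 and second fill within 60 days of run-out (8.2.1, 1c); a 12-month follow-up, taken as days 0–364 (8.5); gap over 60 days (8.3). Assumed: supplies of 30 or 90 days.

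**Formulas.** Let t be the day of the first follow-up MTX claim, c the days from index covered by the pre-index fill, and A the days covered by follow-up fills.

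- Plan: A/(365 - t).
- Whole follow-up: (c + A)/365.

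The second is a weighted average of c/t (weight t/365) and A/(365 - t) (weight (365 - t)/365). The plan's value is therefore too low exactly when c/t > A/(365 - t), and too high when the inequality reverses.

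**Hand records** (90-day fills, overlap shifted forward, truncated at day 364):

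| Fills | Plan | Whole follow-up |
|---|---|---|
| Days -1 and 75, then stop | 90/290 = 0.31 | (89 + 90)/365 = 0.49 |
| Days -25 and 60, then stop | 90/305 = 0.30 | (65 + 90)/365 = 0.42 |
| Day -1, next on day 148, then on time | 217/217 = 1.00 | (89 + 217)/365 = 0.84 |
| Days -30 and -1, then stop | undefined | 150/365 = 0.41 |

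The third patient has 59 uncovered days (89 to 147) and scores perfect adherence. The first and fourth results depend on how overlap is treated. With no shifting they become 165/365 = 0.45 and 89/365 = 0.24. With a 14-day limit the first stays at 0.49, since its overlap is exactly 14 days (75 to 88), and the fourth becomes 103/365 = 0.28.

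**Direction over a grid.** The grid has the initial fill on days -30 to -1, back-to-back fills after the first follow-up fill, and a later gap over 60 days. Differences are plan minus whole follow-up, in percentage points.

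| Supply | Gap before first follow-up fill | Too low | Too high | Range |
|---|---|---|---|---|
| 30 days | 0–14 days | 73% | 27% | -7.2 to +3.0 |
| 30 days | 0–59 days | 42% | 58% | -7.2 to +12.7 |
| 90 days | 0–14 days | 100% | 0% | -16.4 to -3.9 |
| 90 days | 0–59 days | 84% | 16% | -16.4 to +7.6 |

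These are shares of an unweighted grid, not patient frequencies.

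**Simulation.** Assumptions: refill delay exponential with mean 10 days, minus 5; per-fill stop probability 0.25 (90-day) or 0.10 (30-day); at least two fills. The comparator runs from the later of index and the first fill, with carry-in. Means for the discontinued cohort:

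| First fill | Supply | Plan | With carry-in | Relative difference |
|---|---|---|---|---|
| Days -30 to -1 | 90 | 0.447 | 0.554 | 0.447/0.554 - 1 = -19% |
| Days -30 to -1 | 30 | 0.341 | 0.365 | -7% (a second run: 0.345 vs 0.367, -6%) |
| Days -30 to +30 | 90 | 0.528 | 0.583 | -9% |
| Days -30 to +30 | 30 | 0.361 | 0.373 | -3% |
| Days -30 to -1, delay mean 35 | 30 | 0.369 | 0.370 | about 0 |

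In the first row's scenario the persistent cohort scores 0.946 against 0.944. The cohort difference is then 0.946 - 0.447 = 0.50 instead of 0.944 - 0.554 = 0.39.

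**The case against.** A reader might infer that the rule always understates adherence in patients who stop MTX, by about a fifth. The documents do not support that. The late start also drops uncovered days, so the sign depends on refill timing. The 19% requires 90-day supplies, prompt refills and every first fill before index, whereas 1c allows first fills up to day +30. Patients whose first fill is on or after index and who hold no earlier supply get the same value either way. This objection stands.

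The undefined case is also rare. It needs both 1c fills before index, hence a refill within 29 days of the first, and no frequency can be taken from the documents.

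It can further be said that little rests on this measure. Section 8.10 says treatment patterns will be summarized. MTX PDC has no threshold, is not one of the six effectiveness criteria in 8.6.4, and is not among the possible multivariable outcomes in 8.10.2. Because the cohorts are defined by MTX gaps, a lower value in discontinuers is largely built in. All of this limits the consequence. It does not justify the rule: the measure is named under the primary objective, and the plan's own tofacitinib PDC uses the whole follow-up.

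Finally, the rule is explicit and reproducible, and the choice of window is partly preference. Reproducibility does not remove the dependence on which side of index the first fill happened to fall.

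**Conclusion.** The point holds as a timing-dependent bias. Followed as written, the MTX PDC ignores carried-in supply and early uncovered days whenever the initial fill precedes index. It usually lowers the value for prompt refillers who later stop, and raises it for patients with an early gap who then refill on time.

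For the discontinued mean, the scenarios examined run from about 19% too low to no material difference. That range rests on assumed fill sizes, refill delays, stopping rates and shares of pre-index first fills, none of which the documents give. The widening of the cohort difference to 0.50 from 0.39 belongs only to the scenario with 90-day supplies and all first fills before index. Cohort assignment, costs and effectiveness are untouched. The plan should be changed because the measure serves the primary objective and the repair is small, but no main conclusion depends on it.

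**What to change.** Replace the calculation sentence under MTX adherence in 8.6.3 with: *The MTX PDC is the number of distinct days covered by MTX, including supply remaining at index from fills before index, divided by the number of days from the later of the index date and the initial MTX fill (criterion 1c) to the end of the 12-month follow-up. Supply is truncated at the end of follow-up.*

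Add one sentence on how overlapping supply is carried forward, for example the same 14-day limit used for tofacitinib. Without it the new definition does not settle records such as the first and fourth in the table of hand records. Patients with no follow-up claim then receive a value from their carried-in supply.

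The cost is two or three sentences in 8.6.3 and a small programming change. The MTX fills in the 30 days before index are already needed to apply criterion 1c.
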